6.2. Assignment Procedures

Matching and Stratification:

Not applicable

Randomization, Concealment, and Blinding:

Not applicable

Masking (Blinding):

Not applicable

6.3. Intervention – Procedural (if applicable)

Description:

Refer to the Pharmacy Manual for specific instructions regarding requirements for IV bags and labeling, infusion sets, infusion preparation and administration instructions.

Training on Procedural Intervention:

For individuals administering, it will be the unit chief from the PPIU, who has extensive experience administering brexanolone according to the proposed regimen. Nurses on both the PPIU and the Women's Hospital inpatient unit have extensive experience with exactly the administration regimen proposed in this protocol. Prescribers and pharmacists will have been trained and certified in the BRX REMS program.

6.4. Concomitant Therapy:

Subjects may receive standard of care for-patients diagnosed with PPD, including psychosocial interventions. Any concomitant medication determined medically necessary for the welfare of the subject may be given at the discretion of the Investigator at any time during the study, with the caveat that changes to psychotropic medications may be made only as outlined in the paragraph below.

Subjects that are receiving medications administered to treat the symptoms of depression or anxiety (such as antidepressants) must have been initiated at least 14 days prior to dosing and must remain at a stable dose from at least 14 days prior to dosing until completion of the 72-hour assessments. Any new medication for depression or anxiety initiated after the 72-hour assessments are completed must be preceded by a discussion with the investigator and designated REMS physician.

The following interventions will be recorded:

- All medications taken from 60 days prior to informed consent through the final study visit
- All psychotropic medications (including anxiolytics or antidepressants) taken in the previous 6 months prior to informed consent through the final study visit
- All medications used to treat the current episode of PPD regardless of timing through the final study visit
- All nonpharmacological interventions used to treat the current episode of PPD regardless of timing through the final study visit

6.5. Rescue Medications and Procedures (if applicable)

Since subjects will be hospitalized inpatients, and since they will be treated with a GABA positive allosteric modulator, which has known anxiolytic effects, it is not anticipated that anyone would experience a worsening of symptoms; if there was a concern that rescue was required, the response would take the form of decreasing or discontinuing the brexanolone and treating the subject with conservative measures until the response to drug discontinuation could be assessed.

6.6.Compliance Checks

Study drug will be prepared by a pharmacist or designee, administered as a continuous IV infusion, and the dose received will be documented in the study record. There should be no adjustments in dosing except as described in Section 6.1.

6.7.Withdrawal / Discontinuation of Enrolled Participants

Enrolled participants may be withdrawn if new or worsening symptoms or any adverse event suggest that continued participation would place the subject at risk and not be in the subject's best interest.

Subjects may withdraw from the study at any time for any reason without compromising the subject's medical care. The Investigator will also withdraw subjects upon the request of Sage Therapeutics or upon termination of the study.

Subjects who withdraw should, if possible, complete an early termination visit, which includes the assessments for the Hour 72 visit (see Table 3).

The reasons for protocol discontinuation and/or subject withdrawal from the study will be recorded in the study record.

6.8.Voluntary Withdrawal (Drop-Out) of Enrolled Participants

The subjects may voluntarily withdraw participation at any time, for any reason, with no penalty or loss of rights. Reasons for discontinuation will be documented in the database.

7. Study Procedures and Schedule

7.1. Table of Events

Table 3: Schedule of Events

Study Procedure	Screening Period	Treatment Period/Inpatient Stay (Day 1 to Day 4)						Follow-up
		D-14 to 1	D1	D1	D1	D2	D3	
Visit Days		H0*	H4	H8	H28	H60	H72	D30 (±3d)
Hour								
Informed Consent	X							
SCID-5	X							
Demographics	X							
Medical History	X							
Height		X						
Body Weight		X						
Physical Examination ^a	X							
Drug and Alcohol Test ^b	X	X						
Pregnancy Test ^c	X	X						
Clinical lab assessments ^d	X							
ALLO blood sample ^e		X			X		X	
12-lead ECG ^f	X							
Vital Signs ^g	X	X	q4h (while awake) during infusion				X	
C-SSRS ^h	X	X					X	
HAM-D ⁱ	X	X	q4h (while awake) during infusion				X	X
SMDDS ⁱ		X	q4h (while awake) during infusion				X	X
EPDS ⁱ		X	q4h (while awake) during infusion				X	X
STAI (state Y-1) ⁱ		X	q4h (while awake) during infusion				X	X
SCS ⁱ		X	Q4h (while awake) during infusion				X	X
BIMF ⁱ		X					X	X
IDS-SR ⁱ		X					X	X
RRS-10 ⁱ		X					X	X
SHAPS ⁱ		X					X	X
STAI (trait Y-2) ⁱ		X					X	X
EEG Recording ⁱ		X	X	X	X		X	
RS Eyes Open/Closed (8min) ^{i,j}		X	X	X	X		X	

iMotion Recording ^{i,j}		X	X	X	X		X	
Semi-structured Interview ^{i,k}		X	X	X	X		X	
Brexanolone infusion				X				
Continuous pulse oximetry ^l				X				
Continuous HRV collection				X				
Adverse Events				q2h (while awake) during infusion		X	X	
Monitor for excessive sedation				q2h (while awake) during infusion				
Prior/Concomitant medications ^m	X	X				X	X	
Nonpharmacological interventions ⁿ	X	X				X	X	
Exit Interview								X
Compensation (total \$750)	\$50	\$100	\$100	\$100	\$100		\$100	\$200

AE= adverse event; ALLO= allopregnanolone; BIMF= Barkin Index of Maternal Functioning; C-SSRS = Columbia-Suicide Severity Rating Scale; D= Day; ECG= electrocardiogram; EEG= electroencephalogram; EPDS= Edinburgh Postnatal Depression Scale; HAM-D= Hamilton Depression Rating Scale; H=Hour; IDS-SR= Inventory of Depression Symptoms Self-Report; Q= every; RRS-10= Ruminative Responses Scale-10; RS= Resting State; SCID-5= Structured Clinical Interview for Diagnostic and Statistical Manual of Mental Disorders, Fifth Edition; SCS= State Complacency Scale; SHAPS= Snaith-Hamilton Pleasure Scale; SMDDS= Symptoms of Major Depressive Disorder Scale; STAI= State-Trait Anxiety Inventory;

* = All H0 procedures to be completed prior to dosing

a Full physical examination at screening. Symptom-directed physical examination may be conducted at subsequent time point

b Drug and alcohol testing will occur at screening and Day 1 (predose; H0). Drug testing will be done via urine dipstick; alcohol use will be tested via urine dipstick or breath test.

c Serum pregnancy test at screening and serum or urine pregnancy test at Day 1 (predose; H0)

d Safety laboratory tests will include hematology and serum chemistry at all scheduled time points. Coagulation to be assessed at screening only. Laboratory assessments documented in subject's medical record will be considered valid for screening purposes if done within 30 days of infusion

e Laboratory tests for hormone parameters are to be completed within \pm 30 minutes of the scheduled timepoint.

f Performed within \pm 1 hour of the scheduled time point on Day 4

g At all time points, vital signs to include oral temperature (°C), respiratory rate, heart rate, and blood pressure. Heart rate and blood pressure to be collected in supine position at all scheduled time points. Vital signs collected after the initiation of brexanolone will be obtained within \pm 30 minutes of the scheduled time point, unless the subject is asleep between 23:00 h and 06:00 h.

h The "Baseline/Screening" C-SSRS form will be completed at Screening. The "Since Last Visit" C-SSRS form will be completed at subsequent time points
i Hour 0 assessments to be completed on Day 1 prior to the start of the infusion. Subsequent assessments during the inpatient period to be initiated within ± 1 hour of the scheduled time point.
j Performed during EEG recording
k Performed during iMotion Affective Facial Expression Analysis Software recording
l Continuous pulse oximetry to occur for the duration of the infusion. Oxygen saturation need only be recorded in the event of hypoxia (<92% SpO ₂), in which case, the event is to be recorded as an AE
m At screening to include all medications taken within 60 days, all psychotropic medications taken within 6 months, and all medications used to treat the current episode of PPD. At visits subsequent to screening all changes to any medication should be captured. To be eligible, subjects must be on a stable dose of any psychotropic drugs for at least 14 days prior to enrollment.
n All nonpharmacological interventions (eg, psychosocial, psychotherapeutic) used to treat the current episode of PPD should be captured at screening, and all changes should be captured at subsequent visit.

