5.2. Eligibility

Inclusion Criteria:

To be eligible to participate in this study, an individual must meet **all** the following criteria:

- Signed informed consent.
- Ambulatory, female, aged 18-45
- ≤ 8 months postpartum
- Agrees to adhere to the study requirements.
- Onset of depression in 3rd trimester or within 4 weeks of delivery
- Meets DSM-V criteria for major depressive disorder with peripartum onset.
- 17-item HAM-D total score ≥20 at screening
- Stopped breastfeeding or agrees to temporarily stop for 7 days including 4 days of hospitalization and 3 days after
- No new psychotropic drugs during screening and active treatment of study
- Stable use of any current psychotropic drugs for at least 28 days prior to enrollment, with stable dosage for at least 14 days prior to enrollment
- Must be on documented contraceptive.
- Must have a caregiver or family member with them to help care for the subject's child(ren) during the infusion and to be in the room with the subject if the child(ren) are present during the infusion

Exclusion Criteria:

Any individual who meets **one or more** of the following criteria will be excluded from participation:

- Positive pregnancy test at screening or day 1

- Pregnancy that resulted in a stillbirth, termination, or child that was placed for adoption.
- Renal impairment or failure, hepatic impairment or failure, or anemia
- Untreated or inadequately treated hypothyroidism or hyperthyroidism
- Known allergy to progesterone or allopregnanolone.
- Suicide attempt at this episode
- Medical history of schizophrenia, and/or schizoaffective disorder
- Current psychotic symptoms including delusions, hallucinations, or formal thought disorder.
- Concurrent substance abuse
- Exposure to another investigational medication or device within 30 days
- Has previously participated in any study employing brexanolone or SAGE-217.
- Subject is investigative site personnel, sponsor personnel, or an immediate member of their family.
- Has received electroconvulsive therapy during current episode.
- History of seizure disorder
- On anticonvulsant agents
- On benzodiazepines

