7.2. Pre-Screening / Screening (Day -14 to Day 0)

PRE-SCREENING: will be performed by research coordinator, either by phone or in person, following verbal consent from the participant. Information obtained will include self-reported information relevant to inclusion and exclusion criteria (to be confirmed by objective assessment during screening).

SCREENING* (Day -14 to Day 1):

**Sequence of screening procedures not pre-defined after informed consent and HIPAA authorization are obtained.*

Informed Consent and HIPAA Authorization

To be obtained by PI or Study Coordinator prior to any other procedures listed herein.

Demographic/Medical History

Medical history will be collected via a checklist completed by the subject. Age, race, and ethnic origin will be recorded. The diagnosis of PPD will be determined using the SCID-5. Subjects will be specifically asked about the following: depression, anxiety, and other diagnoses per DSM-5. Pregnancy history (including number of pregnancies, number of births, methods of delivery, and birth complications) and PPD episodes will be recorded.

Vital Signs

Vital signs include oral temperature (°C), respiratory rate, heart rate, and blood pressure. Heart rate and blood pressure to be collected in supine position at all scheduled time points as well as in the standing position at specific time points listed in Table 3.

Weight, Height and Body Mass Index

Body weight and height will be measured; body mass index will be programmatically calculated in the study record.

Physical Examination

Physical examinations of major body systems will be undertaken and recorded. Major body systems to be included in the screening physical examination are head, eye, ear, nose and throat, heart, lungs, abdomen, and extremities; as well, cognitive, neurological, and mental status examinations will be performed.

Electrocardiogram

Twelve-lead ECGs will be performed. The Investigator will record if the ECG is normal; abnormal, not clinically significant; or abnormal, clinically significant (CS). If abnormal, details of the abnormality will be provided (e.g., first-degree AV block, bundle branch block). The standard intervals (heart rate, PR, QRS, QT, and QTcF) will be recorded for all ECGs.

Laboratory Assessments

Blood samples will be collected for hematology, serum chemistry, and coagulation. Analytes to be evaluated are summarized in Table 4.

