All blood samples, including those taken for eligibility screening, will be sent to the central laboratory. Laboratory assessments obtained by outside medical clinic will be considered valid if collected within 30 days of infusion start date.

Table 4: Summary of Laboratory Analytes

Hematology	complete blood count (red blood cells, white blood cells with differentiation and absolute values, hemoglobin, hematocrit, reticulocytes, and platelets)
Coagulation (at Screening only)	activated partial thromboplastin time, prothrombin time, and international normalized ratio
Biochemistry	serum electrolytes (sodium, potassium, chloride, bicarbonate or total carbon dioxide, calcium, and phosphorus) renal function tests (creatinine and blood urea nitrogen); liver function tests (total bilirubin, alkaline phosphatase, aspartate aminotransferase, alanine aminotransferase, and gamma glutamyl transferase); thyroid stimulating hormone; total protein; albumin and glucose (fasting or non-fasting)

All clinical laboratory test results outside the reference range will be interpreted by the Investigator as abnormal, not clinically significant; or abnormal, CS. Screening results considered abnormal, and CS at the Screening Visit may make the subject ineligible for the study pending review by the Investigator. Clinically significant abnormal results after screening will be considered and reported as AEs.

Pregnancy Test

All subjects will be tested for pregnancy by serum or urine human chorionic gonadotropin at the during screening.

Drugs of Abuse and Alcohol

Urine assessment for select drugs of abuse will be performed (including amphetamines, barbiturates, benzodiazepines, cannabinoids, cocaine, opiates, and phencyclidine). A positive urine drug screen is exclusionary, unless deemed by the investigator to reflect a prescribed medication. Alcohol will be assessed via breathalyzer or urine dipstick.

Hormones and Biochemistry

Blood samples will be collected and may be analyzed for estrogen, progesterone, progesterone metabolites, thyroid function (TSH, T4, T3), and markers of inflammation.

Columbia-Suicide Severity Rating Scale

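### Recorded or outside laboratory results up to 30 days old are accepted without requiring a draw after delivery, so up to postpartum day 30 a pre-delivery sample can be the only laboratory evidence on anemia, renal and hepatic exclusions

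*Combined protocol and SAP*

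**What the plan says.** The default in section 7.2 (Laboratory Assessments) is a fresh screening draw: "Blood samples will be collected for hematology, serum chemistry, and coagulation". Table 4 lists the analytes. They include a complete blood count with hemoglobin and hematocrit and, under biochemistry, "renal function tests (creatinine and blood urea nitrogen); liver function tests".

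Two sentences let an older result stand in. Table 3 footnote d (section 7.1) reads: "Laboratory assessments documented in subject's medical record will be considered valid for screening purposes if done within 30 days of infusion". Section 7.2 reads: "Laboratory assessments obtained by outside medical clinic will be considered valid if collected within 30 days of infusion start date". Neither mentions delivery.

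Section 5.2 excludes women with renal impairment, hepatic impairment or anemia. It caps time since delivery at 8 months and gives no lower bound. Onset of depression may fall in the third trimester. Another exclusion is "Positive pregnancy test at screening or day 1".

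In Table 3 the row "Clinical lab assessments" is marked at screening only. The Hour 0 blood sample (section 7.3) is for allopregnanolone. The separate hormone sample in section 7.2 "may be analyzed for estrogen, progesterone, progesterone metabolites, thyroid function (TSH, T4, T3), and markers of inflammation"; that list contains no blood count, renal or liver test.

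On abnormal findings, section 7.2 says: "Screening results considered abnormal, and CS at the Screening Visit may make the subject ineligible for the study pending review by the Investigator".

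**The concern.** The three exclusions concern the woman's condition when she starts a 60-hour infusion. A blood sample drawn before delivery cannot show an abnormality that began at or after delivery. Review of abnormal results does not help here, because a later change is not in the earlier sample to be reviewed.

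The plan's own draw does not raise this problem: screening is for women already postpartum, and a positive pregnancy test at screening excludes. The recorded or outside route is where a pre-delivery sample can enter. What is at stake is the quality of one eligibility check in a small group of early-postpartum women. The feasibility counts that form the primary outcomes are not touched.

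**Working it through.** **Inputs**
- Age limit for a recorded or outside result: 30 days before infusion (Table 3 footnote d; section 7.2).
- Time since delivery: at most 8 months, no minimum (section 5.2).
- Blood count and chemistry before dosing: screening only (Table 3).
- Screening period: Day -14 to Day 1 (Table 3; section 7.2), with infusion starting on Day 1.

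**Step 1: when can an accepted sample predate delivery?** Count in whole dates, with delivery on postpartum day 0 and infusion on postpartum day d. The earliest acceptable sample date is d - 30. It falls on a date before delivery when d - 30 < 0, that is, d < 30. The share of the 30-day window lying before the delivery date is (30 - d)/30.

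| Infusion on postpartum day | Earliest acceptable sample (postpartum day) | Share of window before delivery date |
|---|---|---|
| 7 | -23 | 23/30 = 77% |
| 14 | -16 | 16/30 = 53% |
| 21 | -9 | 9/30 = 30% |
| 28 | -2 | 2/30 = 7% |
| 29 | -1 | 1/30 = 3% |
| 30 | 0 (delivery date) | 0/30 = 0% |
| 31 | 1 | 0 |

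Whole dates hide one edge case. For d = 30 the earliest acceptable date is the delivery date itself, and a sample drawn that day before the birth still qualifies. The gap therefore runs up to and including day 30, and from day 31 there is none. The last column is a share of calendar time, not a share of women.

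**Step 2: does another scheduled test close the gap?** No. The Hour 0, Hour 28 and Hour 72 samples are for allopregnanolone. The hormone sample lists none of the relevant tests. Laboratory tests at premature discontinuation (section 7.8) come after dosing has begun and cannot inform eligibility.

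**Step 3: would a shorter window be the cure?** The plan's own draw is at most 14 days old at infusion, or 15 if a Day 0 is counted, so the older-result route reaches 15 to 16 days further back. That difference measures sample age and says nothing by itself about delivery. Under a 14-day limit the earliest sample for an infusion on day 7 would be day 7 - 14 = -7, still before delivery. Only a condition on delivery removes such samples: the earliest acceptable date then becomes max(0, d - 30), after the birth.

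**Step 4: how many women?** This cannot be computed. The documents give neither the distribution of time since delivery at infusion nor the rate at which older results will be used.

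**The case against.** The strongest reply is that the case needs several conditions together: infusion by postpartum day 30, use of a recorded or outside result, a sample taken before delivery, no later result on record, and no fresh draw. The two sentences permit an older result and do not oblige anyone to use it. An older report can stand in only for the analytes it contains; Table 4 is a long panel, and nothing waives what the report lacks. Other safeguards remain: birth complications are recorded and a full physical examination is done at screening, participants consent to access to their medical records (section 10.2), prescribers are REMS-certified (section 6.3), and pulse oximetry is continuous during infusion. The exclusions themselves are not tied to any particular sample.

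Most of this stands and is why the point is small. It does not remove the gap, because none of these safeguards is a blood test after delivery. One might also read section 7.2 as still requiring a fresh draw sent to the central laboratory, but calling an older result valid for screening has little practical use unless it can replace that draw.

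A further objection is that any sample misses later events, and that one taken just after birth would pass for an infusion on day 29 or 30. That is correct and limits what the fix achieves.

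A reader might infer that a pre-delivery sample could be the only evidence of any kind, or that it could clear the whole panel. The documents do not support either reading, given the safeguards above and the analyte limit.

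**Conclusion.** The point holds as a minor gap in a stated validity rule. For infusions up to and including postpartum day 30 (on day 30 only through a sample drawn on the delivery date before the birth), a pre-delivery sample can be the only laboratory evidence bearing on the anemia, renal and hepatic exclusions, for the analytes in that report.

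This rests on two readings: that a result called valid may replace the scheduled draw, and that no one chooses to repeat it. The safety gain from closing the gap is small, the number affected among the 12 planned enrollees cannot be estimated, and it may be zero.

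A reader might go further and infer that the trial's screening is unsafe, or that its feasibility results would be distorted. The documents support neither. They do not show that any woman would be affected, and the primary outcomes count analyzed recordings, completions and withdrawals. Nor is the 30-day allowance itself an error; the version 4 change log mentions 14 days, but a difference from a change log is not a fault in the current text.

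**What to change.** Keep the 30-day allowance. Add to Table 3 footnote d, and to the outside-laboratory sentence in section 7.2: *and after delivery; otherwise the scheduled screening draw is used.*

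The cost is one clause in two places and, for some early-postpartum women who would have used an older result, at most one blood draw that the schedule already contains. The change ensures that an accepted result postdates delivery. It does not address abnormalities that arise after a post-delivery sample; that would need a shorter window or a predose draw, which is not proposed here.
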